4. At endline, the provider competency level and the performance level of the *full* package group will be significantly higher than those of the training-only group.

2. Background and rationale:

Disease Burden: Postpartum Hemorrhage and Neonatal Apnea/Asphyxia

Postpartum hemorrhage (PPH) is the leading cause of maternal mortality worldwide (1), accounting for one-quarter of maternal deaths (2). The global incidence of postpartum hemorrhage has been reported at 10.8%, with a range from 7.2% in Oceania to 25.7% in Africa (3). About one-quarter of global neonatal deaths are due to birth

¹ Note: These rates or proportions may increase between baseline and midline due to better reporting, and we expect these to decrease due to the intervention between midline and endline.

asphyxia and another one million stillbirths occur during the intrapartum period—these stillbirths are often misclassifications of secondary apnea. A large proportion of these two million deaths could be averted with the timely and correct use of neonatal resuscitation (4).

Uganda, the setting for this study, has a maternal mortality ratio of 310/100,000 live births (5) and according to regional estimates, about 34% of these deaths are due to postpartum hemorrhage (6). The national neonatal mortality rate is 29 per 1000 live births and the stillbirth rate is 25/1000 (7). It would be expected that 28% of neonatal deaths would be due to asphyxia/apnea in this setting (6). The proportion of births with a skilled attendant is about 80% in urban areas and 40% in rural areas (7).

Neonatal Asphyxia/Apnea Interventions

The American Academy of Pediatrics and partners developed “Helping Babies Breathe” (HBB) (8), a training package designed to increase newborn survival by improving recognition and basic interventions for babies who do not breathe at birth. HBB focuses on routine care after healthy birth, initial steps of helping the newborn to breathe at birth, ventilation with bag and mask, and ongoing care after resuscitation, with use of a simulator to practice these skills. Results of HBB field testing in Kenya, Pakistan and India demonstrated improved knowledge and skills in providers and helped refine the educational materials, which are currently in use in 55 countries.

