2) **Study procedures, including sequence and timing.**

Figure 1 presents an overview of activities related to the intervention and its evaluation.

Figure 1 – Intervention and Evaluation Activities

Saving Lives on the Day of Birth: Building and Sustaining Capacity of Frontline Health Workers in Uganda

Intervention Description – More Detailed

Intervention: Bleeding After Birth

The intervention starts with all study arms receiving a one-day, facility based PPH prevention simulator-assisted training of all providers who attend births in a facility with the simulators being left onsite for ongoing practice:

The first module of the twinned training, “Bleeding after Birth” (BAB), uses graphic materials and simulation, to teach providers psychomotor and decision making skills to prevent, detect, and manage PPH including both treatment and timely referral as appropriate. To ensure retention and improved performance, for two of the study arms training will be followed by ongoing **low dose, high frequency (LDHF) simulation practice** conducted by Peer Practice Coordinators at the facility. (The “training-only” study arm will have the PPH simulator left at the facility with a recommended schedule for practice, but no PPCs designated to coordinate the training.) PPCs will be providers already posted at the facility who have undergone the training and have agreed to take on the role to support ongoing training in their facilities. After the initial training module is delivered, two providers per facility will be invited to participate in improving care for PPH and newborns by become PPCs. Two will be selected to address turnover and ensure simulated practice is conducted on a routine basis. After training in the first module (BAB), the PPCs will undergo a half-day training to enhance their skills related to peer-led training.

To test the added value of **mobile phone support**, providers or PPCs in one of the two intervention arms receiving the PPC LDHF intervention will receive ongoing SMS and voice support during the LDHF practice period. PPCs will be provided ongoing mobile support as reminders for practice and to maintain their clinical and training-related capacities. This technology will be used to provide remote reinforcement, assessment and real-time performance support by master trainers to PPCs. In addition, SMS messaging will be used for providers in this intervention arm to provide clinical content and practice reminders.

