2. Provider competencies and performance will not decline (i.e. will be non-inferior) between midline and endline in the *partial* package group.
3. At endline, the provider competency level and the performance level of the *partial* package group will be significantly higher than those of the training-only group.
4. At endline, the provider competency level and the performance level of the *full* package group will be significantly higher than those of the training-only group.

Hypotheses 1 and 2:

This is a non-inferiority analysis. Two-sided 90% confidence intervals (CI) for the difference in average knowledge and competence scores between midline and endline will be constructed, separately for full and partial package groups. Non-inferiority will be determined comparing the upper bound of the 90%CI for the difference between the 2 time points to the pre-specified non-inferiority margin of 0.06 (22). If the CI's upper bound is less than the predefined margin, then we are able to claim non-inferiority of the endline knowledge scores to the midline knowledge at a 0.05 level of significance.

We will first examine the differences in sample means of knowledge scores between midline and endline not adjusted for any potential confounding variables. The confidence intervals for the knowledge scores will be calculated using generalized linear models with knowledge and competencies as the dependent variables and time variable (endline vs. midline) as the primary independent variables. To account for repeated observations within providers at midline vs. endline, we will use robust Huber/White estimate of variance implemented in STATA through 'vce' (cluster) option. In addition, adjusted 90% CI for the difference in means will be constructed by adding provider- and facility-level factors in the model.

Hypotheses 3 and 4:

We will examine differences in competencies and performance at endline between the 3 study groups using generalized linear models. The dependent variables in these models will be:

- 1) knowledge and competency scores,
- 2) proportion of women who received **oxytocin** (at correct dosage) within one minute of a vaginal birth,
- 3) proportion of women whose placenta was inspected within 16 minutes, and
- 4) proportion of newborn checked for breathing within 1 minute.

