The primary independent variable will be the study group represented as 2 indicator variables for full and partial training package with training-only as the reference group. For these hypotheses, we will only use endline data. Additional variables, related to provider- and facility characteristics predictive of these outcomes, such as cadre, number of years of provider's experience, and number of prior births attended in last 90 days, will be also included in the model. Analysis of residuals will inform whether the assumptions of the generalized linear model, such as normality and homoscedasticity of residuals as well as linear fit, are satisfied.

Additional analyses will include:

1. At baseline, midline and endline we will collect data from **all study facilities** consisting of service delivery statistics, and facility inventory. These data will be analyzed using population-average marginal generalized linear models estimated using generalized estimating equations (GEE) with exchangeable working correlation structure to account for repeated observations within facilities. The dependent variable will be service delivery statistics. The independent variables will include time (represented as 2 indicator variables for midline and endline with baseline as the reference group), study group (represented as 2 indicator variables for full and partial training groups with training-only as the reference group), and interaction terms (study group by time). The interaction terms will be examined to assess whether there are differences between study groups that change significantly over time.
2. Providers who are trained will keep **logs of their practice sessions**. This is process evaluation data. These data (for example on number of times a scenario is practiced) will be compared across the three study groups using generalized linear models with Poisson or Negative Binomial distribution for the outcome.
3. **Routinely collected data from health facility registers** (recorded daily but aggregated monthly) on services provided to clients and health outcomes (discharge, or deaths and stillbirths) will be analyzed using longitudinal data analysis to account for repeated observations at each facility. This will be for population-averaged marginal generalized linear models using generalized estimating equations (GEE) and exchangeable working correlation structure.

Qualitative Analysis

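### Full and partial packages differ only in mobile support, whose added value the plan says it tests, but no hypothesis, sample size or pre-specified contrast compares them on competency or performance

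*Combined protocol and SAP*

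**What the plan says.** **Purpose.** The BAB intervention description in Section 4b(2) states the aim as "To test the added value of" mobile phone support. Providers or coordinators "in one of the two intervention arms receiving the PPC LDHF intervention will receive ongoing SMS and voice support during the LDHF practice period". Table 1 shows that arms 2 and 3 share training and peer-led practice, and that only arm 3 has the mobile component.

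**Hypotheses.** Hypotheses 1 and 2 (Sections 1 and 4b(5)) concern change from midline to endline inside one arm; the intervals "will be constructed, separately for full and partial package groups". Hypotheses 3 and 4 are between-arm, and each has the same comparator: the "package group will be significantly higher than those of the training-only group".

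**Model.** Section 4b(5) introduces the analysis of Hypotheses 3 and 4 broadly: "We will examine differences in competencies and performance at endline between the 3 study groups using generalized linear models". The coding is "study group represented as 2 indicator variables for full and partial training package with training-only as the reference group", and only endline data are used. The GEE model for service statistics also takes training-only as reference. Neither states a full-minus-partial contrast.

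**Practice logs.** Log counts are to be compared across the study groups (Section 4b(5)), but Section 4b(2) has logs kept only in the full and partial arms.

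**Sample size.** Table 5 note (b) sizes an intervention group against training-only at endline. Table 4 nonetheless expects full to exceed partial by 10 points at midline (75% against 65%) and at endline (70% against 60%).

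**The concern.** The contrast that isolates mobile support is full against partial. The plan announces that question, builds an arm for it and assumes an effect, but does not say how the effect will be estimated, on which outcomes, at which time or with what inferential status.

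Left unplanned, the natural substitute is to set two comparisons with training-only side by side. One significant and one non-significant result does not show that the packages differ, and two significant results do not show that they are alike. The unequal arms add a tilt: full against training-only rests on 378 and 189 births at endline, partial against training-only on 189 and 189.

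Section 4b(10) says that the results will inform recommendations to government on scale-up. Whether to pay for a mobile layer on top of peer practice is part of that decision.

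**Working it through.** **1. Which comparison was sized?** Inputs from Table 5 note (b): 50% against 65%, 80% power, ICC 0.01. Assumed: two-sided alpha 0.05 (the note gives none) and the 54 facilities of note (a).

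- Two-proportion formula: 170 per arm; with continuity correction, 183.
- Design effect: 1 + (189/54 − 1) × 0.01 = 1.025.
- 183 × 1.025 ≈ 188, against the stated 189.

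The plan's figure therefore reproduces as a package against training-only. The 99 births in Table 5 for a midline-only comparison match 75% against 55% (98 with continuity correction), which is full against training-only.

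**2. What would full against partial need?** For 80% power at the Table 4 values:

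| Time | Rates | Births per arm | With continuity correction | Also with ICC 0.01, 54 facilities |
|---|---|---|---|---|
| Endline | 70% v 60% | 356 | 376 | about 399 |
| Midline | 75% v 65% | 329 | 349 | about 369 |

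The plan has 378 (full) and 189 (partial) at each time.

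**3. Precision with the planned numbers, endline.** Ignoring clustering:

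- SE = √(0.70×0.30/378 + 0.60×0.40/189) = √(0.000556 + 0.001270) = 0.0427.
- 95% half-width = 1.96 × 0.0427 = 8.4 points.
- Power is about 66% with the pooled variance under the null, and about 65% with the unpooled SE throughout.
- The difference detectable with 80% power is about 12 points, against the 10 expected.

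*Clustering by facility, ICC 0.01, 54 facilities per arm assumed:* design effects are 1 + (378/54 − 1) × 0.01 = 1.06 and 1.025; power is about 65% (pooled). With 36 facilities per arm (9 in each of 4 districts) it is about 64%.

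*Clustering by district.* Section 3 draws arms within groups of three districts, two groups in each of two regions, so there are 4 districts per arm. Births per district are 378/4 = 94.5 and 189/4 = 47.25. The plan gives no district-level ICC; applying 0.01 there is an assumption:

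- Design effects: 1 + 93.5 × 0.01 = 1.935 and 1 + 46.25 × 0.01 = 1.4625.
- SE = √(0.000556×1.935 + 0.001270×1.4625) = 0.0542.
- Half-width = 1.96 × 0.0542 = 10.6 points.
- Power = Φ(0.10/0.0542 − 1.96) ≈ 45%.
- With a t reference on 4 + 4 − 2 = 6 df (critical value 2.447), the half-width is about 13 points and power about 34%.

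| Assumed district ICC | SE | Half-width (normal) | Power (normal, unpooled) |
|---|---|---|---|
| 0.005 | 0.0488 | 9.6 points | 54% |
| 0.01 | 0.0542 | 10.6 points | 45% |
| 0.02 | 0.0636 | 12.5 points | 35% |

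**4. Midline.** At 75% against 65%, power ignoring clustering is about 70% (pooled). With ICC 0.01 at district level, SE = √(0.1875×1.935/378 + 0.2275×1.4625/189) = 0.0522, the half-width is 10.2 points and power about 48%.

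**5. How the side-by-side reading would behave.** At Table 4 endline values with ICC 0.01 by facility, power is about 99% for full against training-only (70% v 50%, 378 and 189) and about 49% for partial against training-only (60% v 50%, 189 and 189). A split verdict is therefore about as likely as not. Part of it comes from arm size: ignoring clustering, the two SEs are √(0.21/378 + 0.25/189) = 0.0433 and √(0.24/189 + 0.25/189) = 0.0509.

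**The case against.** A reader might infer that no model compares full with partial, or that the trial cannot answer the mobile question. The documents support neither.

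- The practice-log model is in effect a full-against-partial comparison, because only those arms keep logs, and practice frequency (Objective 1) is what reminders and weekly calls target most directly. This stands. It is a process measure, however, and says nothing about competency or care given.
- The endline model is introduced as examining differences among all three groups. A reference category is a parametrisation, not a limit on reporting, and full minus partial is the difference of its two coefficients. This also stands: the gap is in pre-specification, not estimability. Nor does the plan propose to infer added value from two separate significance tests; that is a risk left open.
- Isolating mobile support is not the study's only purpose. The overall hypothesis concerns both packages, Section 4b(10) speaks of graded intensity, and Section 4b(1) notes that the mobile component was still under negotiation because of a moratorium. That is a fair reason not to make the contrast confirmatory. It is not a reason to leave it unstated, since Section 9a counts the effect of the SMS component among the things being studied.
- A power of 66% and a half-width of 8.4 points flatter the contrast, because they ignore assignment by district. This is right, and the district-level range is the one to report.

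**Conclusion.** The point holds in this form: the plan states that it tests the added value of mobile support, but no specific hypothesis, sample size or pre-specified contrast compares full with partial on any competency or performance outcome. The comparison is available from data and a model already planned.

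Its precision is limited. For the oxytocin outcome at endline, power to detect the plan's own 10-point gap is about 66% ignoring clustering and about 65% at ICC 0.01 by facility. It is about 35% to 54% if an ICC of 0.02 to 0.005 applies at district level, and lower with a t reference on 6 df. At a district ICC of 0.01 the half-width is about as large as the expected gap or larger (10.6 points, or about 13 with the t reference). A non-significant contrast must therefore not be read as showing no added value.

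These figures assume two-sided alpha 0.05, Table 4 rates, the Table 5 birth counts and equal births per cluster. The district ICCs are assumptions. No comparable figure can be given for the neonatal primary outcome, because the plan gives no expected number of babies not breathing at birth.

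**What to change.** In Section 4b(5), add to the between-arm model a linear contrast, full minus partial, reported with its 95% CI, and name it as the estimate of the added value of mobile support. Specify:

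- **Outcomes:** each dependent variable listed for Hypotheses 3 and 4, plus the neonatal primary outcome (babies not breathing at birth who are breathing or ventilated by one minute), which that list omits.
- **Times:** endline, and also midline, when mobile support has just ended. Endline comes six months later and measures persistence.
- **Standard errors:** a method that accounts for assignment by district and for having only four districts per arm.
- **Status:** secondary or exploratory, with the limited power stated beforehand and a sentence that a non-significant result is not evidence of no added value.

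If the sponsor does not want this contrast, the wording in Section 4b(2) should stop describing the design as a test of mobile support.

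Cost: one post-estimation contrast, a refit of the same model to midline data, and one more dependent variable from births already observed. There are no new data and no change to the arms or sample size. Label: free improvement.
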